## APPENDIX D: Questionnaire 1: Case History Form

### Medical / Hearing History Questionnaire

Name: \_\_\_\_\_

Date of Birth: \_\_\_\_\_

Gender: \_\_\_\_\_

Length of time as a police officer: \_\_\_\_\_

Handedness: \_\_\_\_\_ Shoot with: \_\_\_\_\_

How often do you shoot for certification, annually (occupational)? \_\_\_\_\_

Communication radio location: \_\_\_\_\_

Do you have an existing hearing problem?	Yes	No	Unknown
If you have a hearing problem, has it been:	Gradual	Lifelong	Sudden
Have you ever had your hearing tested?	Yes	No	If yes, when? _____
Have you recently experienced pain in either ear?	Yes	No	Left Right Both
Have you recently experienced drainage from your ear?	Yes	No	Left Right Both
Have you recently experienced ear fullness of discomfort?	Yes	No	Left Right Both
Have you recently experienced dizziness?	Yes	No	Left Right Both
Do you experience tinnitus (ringing) in your ears?	Yes	No	Left Right Both Center
If yes, how often?	Rarely (few times a year) Several times a year Several times a month Several times a week Daily		
Have you ever been to an ear specialist?	Yes	No	
Have you ever had ear surgery?	Yes	No	
Do you have frequent ear infections?	Yes	No	
Do you have sinus problems?	Yes	No	
Do you have allergies?	Yes	No	
Do you currently use prescription or over-the-counter drugs?	Yes	No	

Have you ever had kidney disease?	Yes	No
Have you ever had meningitis?	Yes	No
Do you have diabetes?	Yes	No
Do you have high blood pressure?	Yes	No
Do you experience headaches?	Yes	No
Have you experienced head trauma?	Yes	No
Do you have facial numbness?	Yes	No
Do you shoot recreationally (i.e. hunting)?	Yes	No
If yes, how often do you shoot recreationally?	Rarely (few times a year) Several times a year Several times a month Several times a week Daily	
Is hearing protection used when you shoot recreationally?	Never (0% of time) Minimally (~25% of time or less) Moderately (~50% of time) Often (~75% of time) Always (100% of time)	
Do you participate in loud activities (music, concerts, motorcycle)?	Yes      No What types of activities? <hr/> <hr/> <hr/>	
If yes, how often do you participate in these activities?	Rarely (few times a year) Several times a year Several times a month Several times a week Daily	
Is hearing protection used when you participate in these activities?	Never (0% of time) Minimally (~25% of time or less) Moderately (~50% of time) Often (~75% of time) Always (100% of time)	

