5.2 Missing Data

Every attempt will be made to ensure data completeness. We do not anticipate much loss to follow-up because of the relatively short time follow-up interval. Conservatively, we would estimate that fewer than 5% of subjects will drop out/withdraw from the study. The participant will be withdrawn from the study follow-up and procedures if the participant withdraws consent, or the sponsor decides to close the study.

Data loss, if any, would almost likely be due to subjects refusing to complete or not returning at all for the post-shooting assessment of PTS 30 days (+/- 3 days). If the subject reschedules the post-shooting appointment for a later date for any reason, and if this delay is within 30 days of the scheduled date, the data will be considered valid and used in the efficacy analysis. Any measure outside this time window of +30 days will be defined and considered as missing data.

Missing PTS at 30 days will be imputed using SAS PROC MI procedure within each treatment group using the distribution implied by the non-missing data for the specific treatment group. The SAS code below using MICE via the Fully Conditional Specification (FCS) statement will be used to impute the missing data under the missing at random (MAR) assumption.

```
PROC MI DATA=X SEED=<value> NIMPUTE=10 OUT=MI_OUT1 NOPRINT;
  CLASS GROUP;
  VAR AGE PTA LSurg....;
  FCS LOGISTIC(PTS);
  RUN;
```

The estimates of the analysis of the 10 imputed datasets will be then combined following Rubin's rules using PROC MIANALYZE procedure in SAS which will be of the form:

```
PROC MIANALYZE PARMs=GMPARMS COVB=GMCOVB PARMINFO=GMPINFO WCOV BCOV
  TCOV; / *dataset "gmparms" contains the estimates and associated standard errors
  for the mean parameters from each of the M=10 imputed data sets.
  dataset "gmcovb" contains the asymptotic covariance matrices
  dataset "gmpinfo" contains parameter info*/
  MODELEFFECTS group;
  RUN;
```

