The lower (l_D) and the upper limits (u_D) of $100(1-\alpha)\%$ confidence interval for D will be calculated as:

$$l_D = D - \sqrt{(p_1 - l_1)^2 + (u_2 - p_2)^2}$$

$$u_D = D + \sqrt{(p_2 - l_2)^2 + (u_1 - p_1)^2}$$

To provide an estimate of treatment effect a supportive logistic regression analysis will be done with covariates: age, pre-existing hearing loss dichotomized to normal to minimal hearing loss and slight to mild loss, noise exposure history dichotomized to high risk and low risk, average post-shooting.

Sensitivity analysis of the primary endpoint

The potential impact of missing primary endpoint data will be explored in sensitivity analyses using multiple imputation. Two sensitivity analyses performed:

Sensitivity 1: MI analysis under the missing not at random assumption (MNAR)

Sensitivity 2: Logistic regression tipping point analysis under the assumption of data missing at random.

Sensitivity 1.

Proc MI procedure in SAS will be used to impute missing data for study treatment groups using the distribution implied by the non-missing officer data within the placebo group. The SAS code to impute data for Sensitivity analysis 1 under the MNAR assumption will be of the form:

```
PROC MI DATA=X SEED=<value> NIMPUTE=10 OUT=MI_OUT1 NOPRINT;
CLASS GROUP;
VAR AGE PTA LSurg....;
FCS LOGISTIC(PTS);
RUN;
```

Post imputation each of the imputed 10 datasets will be analyzed using the same approach as for the primary outcome measure. The estimates of the analysis of the 10 imputed datasets will be then combined following Rubin's rules using PROC MIANALYZE procedure in SAS which will be of the form:

```
PROC MIANALYZE PARMs=GMPARMS COVB=GMCOVB PARMINFO=GMPINFO WCOV BCOV
TCOV; / *dataset "gmparms" contains the estimates and associated standard errors
for the mean parameters from each of the M=10 imputed data sets.
dataset "gmcovb" contains the asymptotic covariance matrices
dataset "gmpinfo" contains parameter info*/
MODELEFFECTS INTERCEPT AGE PTA LSurg....;
RUN;
```

Sensitivity 2.

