Analysis of variance (ANCOVA) will be used for comparison of outcome measures between each of the ZNS groups and placebo study group after controlling for baseline value, age, pre-op hearing dichotomized to: normal to minimal hearing loss and slight to mild loss, noise exposure history dichotomized to: high risk and low risk, average post-shooting TTS.

Statistical analyses will be conducted using the SAS software (SAS Institute Inc., Cary, N.C.,

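### The MAR imputation program in SAP 5.2 does not implement its own text: arm and PTS are not visible in the model, and LSurg is undefined

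*SAP*

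**What the plan says.** SAP 5.2 gives the rule for the missing-at-random (MAR) analysis: a missing 30-day PTS result "will be imputed using SAS PROC MI procedure within each treatment group", from the observed data of the arm concerned. It then presents a PROC MI program as the code for that purpose. This is a firmer commitment than the indicative wording it gives to the MIANALYZE step and to Sensitivity 1. The program contains:

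- a `CLASS` statement naming GROUP only;
- a variable line that opens "VAR AGE PTA LSurg" and ends in dots;
- an imputation line that opens "FCS LOGISTIC(PTS";
- 10 imputations and no `BY` statement.

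Protocol 12.2.2 (Missing Data) repeats both text and code.

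The same PROC MI block is printed twice more in SAP 7.1.1 and in Protocol 12.2.1. One copy is for Sensitivity 1, where missing values are to be imputed "using the distribution implied by the non-missing officer data within the placebo group". The other is Step 1 of Sensitivity 2. Only Step 2 of Sensitivity 2 contains a `by group` statement.

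On covariates, the supportive logistic regression in SAP 7.1.1 uses age, prior hearing loss in two classes, noise history in two classes, and an unfinished post-shooting term. The ANCOVA in SAP 7.1.2 names that term in full as "average post-shooting TTS". Neither list has a surgical covariate. On missingness, SAP 5.2 expects fewer than 5% of subjects to be lost, and SAP 2.7 expects none.

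**The concern.** A pre-specified imputation model should tell the programmer what is imputed, from which predictors, and how the arm enters. Here the prose and the program give different answers. Read as printed, no term separates the arms. The outcome itself is missing from the two statements where it is needed. One of the three named predictors has no meaning in the visible text.

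The role of the arm is what could matter numerically. If it is left out, a missing ZNS officer and a missing placebo officer receive the same average PTS risk, and the estimated benefit is pulled towards zero. LSurg is a separate defect: it does not cause pooling, but it leaves the model undefined. Meanwhile the Visit 3 threshold shift is not printed as a predictor, although every randomised officer must have one, because TTS is the enrolment criterion in Protocol 3.1b.

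**Working it through.** **1. Text against program**

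| Point | Text | Printed code |
|---|---|---|
| Arm | Each arm from its own data | No `BY GROUP`; GROUP in `CLASS` but not visible in `VAR` |
| Outcome | PTS is imputed | PTS in neither `CLASS` nor visible `VAR` |
| Predictors | Age, baseline hearing, noise history, post-shooting shift (SAP 7.1.1 and 7.1.2) | AGE, PTA, LSurg, dots |
| Sensitivity 1 | Drawn from placebo data | Same block as the own-arm MAR analysis |

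Logistic FCS imputation needs PTS as a classification variable on the variable list, so the block would not run as printed. This follows from the procedure's syntax, not from a test run.

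**2. The plan's own power figure.** Inputs from SAP 2.7: 66 per arm, 50% v 25%, one-sided 0.025. Fisher's exact test by the Walters arcsine approximation, with e = 1/(2 × 66):

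power = Φ{2√(66/2) × [asin√(0.50 − e) − asin√(0.25 + e)] − 1.96} = 80.5%.

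This agrees with the SAP. Full enumeration of the exact test gives 81.3%.

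**3. Expected difference if the arms are pooled.** Assume the same missing share m in both arms, missing completely at random, and no covariates. With 1:1 allocation the pooled risk is (0.50 + 0.25)/2 = 0.375. The expected rate in an arm is (1 − m) × p + m × 0.375, so the difference is (1 − m) × 25 points.

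- m = 3%: 24.25 points
- m = 5%: placebo 0.95 × 0.50 + 0.05 × 0.375 = 49.4%; ZNS 0.95 × 0.25 + 0.05 × 0.375 = 25.6%; difference 23.75 points; odds ratio 0.353 instead of 0.333
- m = 10%: 22.5 points
- m = 20%: 20.0 points

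In officers, at m = 5% about 0.05 × 66 = 3.3 per arm are missing, and pooling moves 3.3 × 0.125 ≈ 0.4 expected events per arm.

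**4. Power.** Simulation of 20,000 trials per setting, 10 imputations, Rubin's rules, one-sided 0.025:

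| Missing | Risk difference: own-arm v pooled | Log odds ratio: own-arm v pooled |
|---|---|---|
| 5% | 84.1% v 81.1% | 82.9% v 79.9% |
| 10% | 82.1% v 76.3% | 80.7% v 74.5% |
| 20% | 76.9% v 61.6% | 75.2% v 58.8% |

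The loss at 5% is about 3 points on either scale. The 10% and 20% rows lie beyond what the plan expects and show only how the loss grows.

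**5. Under equal rates.** The pooled risk equals each arm's risk, so the expected difference stays at zero. Pooling costs power but does not favour ZNS.

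**6. If GROUP is in the model.** Each arm has its own intercept, imputed values follow that arm's rate, and the shrinkage largely disappears. The covariate effects would still be common to both arms, which is not quite what the text describes.

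**The case against.** A reader might infer that the SAP will pool the arms and dilute the treatment effect. The documents do not support that. The variable line ends in dots and omits even PTS, so it is plainly abbreviated. Declaring GROUP in `CLASS` makes sense only if GROUP was meant as a model term. The prose asks for arm-specific imputation. Run literally, the block would fail rather than pool silently. These points stand: pooling is possible, not established.

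A reader might also infer that the trial does not collect LSurg. That cannot be shown. The start of the SAP's abbreviation list was not available for this review, so an entry under L may exist. Protocol Appendix D does ask "Have you ever had ear surgery", and whether that is LSurg is unknown. Carry-over from a surgical trial is the likelier explanation, given the pre-operative hearing term in SAP 7.1.2 and the contralateral-ear table titles in SAP 12.1.

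The size is small at the plan's expected missingness, and nil if nothing is missing. The power figures use Rubin-pooled tests, whereas the primary test is Fisher's exact, and the SAP does not say how Fisher results from imputed data are combined. Bias in the primary test itself is therefore not demonstrated.

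Quality control in SAP 11 makes an unnoticed error less likely. But SAP 11.1 has the detailed specifications written after the SAP is final, so the model would be settled outside the pre-specified plan. Nor can the dots explain everything: one identical block cannot implement both own-arm and placebo-based imputation.

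**Conclusion.** The point holds as a mismatch between a stated analysis and its program, and as an incompletely specified imputation model. It does not hold as proof of a biased trial result. The dilution is conditional on a programmer completing the list without GROUP. In that case the expected difference falls from 25.0 to 23.75 points at the 5% ceiling, with about 3 points of power lost and no type I inflation under equal rates. This assumes the plan's 50% v 25%, equal missingness in the arms, data missing completely at random and no covariates. The plan has little power in reserve (80.5%, or 79.4% with the futility rule in SAP 9), so the ambiguity should be removed, but the matter is one of clarity more than of large effect.

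**What to change.** In SAP 5.2 and Protocol 12.2.2:

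1. Put PTS in both `CLASS` and `VAR`.
2. Make the arm explicit. One option is `BY GROUP` with few predictors: at 5% missing only about 0.95 × 66 × 0.25 ≈ 16 ZNS events are expected, roughly four per predictor with four predictors. The more stable option is one model that names GROUP, with the sentence on own-arm imputation amended to match.
3. Delete LSurg and replace the dots with variables already collected: age, baseline 2-6 kHz threshold (Visit 2), post-shooting shift (Visit 3), and the noise stratum if the low-noise group is not too sparse.

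In SAP 7.1.1 and Protocol 12.2.1, remove LSurg and state the variables wherever the block or its model line recurs in Sensitivity 1 and 2. Print separate code for Sensitivity 1 that draws from the placebo data. Test-run each block on dummy data before sign-off.

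The cost is a few lines of SAS and matching wording in the two documents. No new data are needed.

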6 STUDY SUBJECTS

6.1 Disposition of Subjects

Participant disposition data will be summarized by treatment group and overall for the ITT Sample Set. The number randomised, treated, completed or discontinued from the study, including reasons for discontinuation as well as the number of subjects in each sample set and participant treatment status will be summarized descriptively.

All disposition data will be listed. Inclusion and exclusion criteria will also be listed.

6.2 Demographics Characteristics

Demographic characteristics will be summarized descriptively by treatment group for the Safety Sample Set, including:

- Age (years) at time of consent
- Sex
- Ethnicity
- Race

Demographics characteristics will be listed.

6.3 Medical History

Medical history will be coded with Medical Dictionary for Regulatory Activities (MedDRA) version 24.0 and summarized by System Organ Class (SOC), Preferred Term (PT), and by treatment group with counts and relative frequency based on the Safety Sample Set. A participant will only be counted once in an SOC and an SOC/PT combination.

All medical history data will be listed.

6.4 Concomitant Medications

Concomitant medications are defined as all medications (excluding study dose) taken on or after the date of first dose administration up to and including the date of the post training Day 30 visit (Visit 5).

Medications that started before the date of first dose and are ongoing after the date of first dose will be considered as concomitant medications.

Medications will be coded using the Anatomical Therapeutic Chemical (ATC) classification codes and preferred drug name according to the World Health Organization (WHO) Drug Global B3, (March 2021). Summary table will be provided for concomitant medications for the Safety Sample Set, presenting the number and relative frequency of subjects by treatment group, and will be sorted in alphabetical order of ATC Level 2 and then PT in the overall column. For each participant, the medication will be counted only once within a given ATC level 2 and only once within a given preferred drug name level. A participant may appear more than once if she has more than one concomitant medication coded under different ATC categories.

Concomitant medications will be presented in a listing.

6.5 Treatment Administration

The number of doses taken will be summarized by treatment group and overall for the Safety Sample Set and include

- Number and percentage of subjects who received the dose

Dose administration information will be listed for all safety subjects.

6.6 Protocol Deviations

Protocol deviations will be summarized for the Safety Sample Set by type of deviation. Protocol deviations for all subjects who signed an informed consent will be entered into Pharm-Olam's Clinical Trial Management System. Examples of deviation types may include but are not limited to:

- Inclusion/exclusion criteria not met
- Informed consent
- Randomization
- Essential/Study Documents
- Investigational product administration and handling
- CRF/source data
- Sample/tests handling
- Equipment/Facilities
- Visit procedures
- Other

Protocol deviations will be reviewed by University of Akron and Pharm-Olam medical and clinical (including statistical) personnel and classified as major or minor deviations at a blinded data review meeting prior to database lock.

Major protocol deviations are defined as those that may significantly impact the quality (i.e., completeness, accuracy, and reliability) or integrity of key trial data; or indicates systemic problem within the study or its conduct; or that might significantly impact the rights, safety or welfare or trial subjects.

Protocol deviations will be presented in each deviation category as a major or minor deviation by treatment group. The total count of protocol deviations within each treatment group will be used as the denominator for relative frequency in this table. All protocol deviations will be presented in a data listing.

7 EFFICACY ANALYSES

All efficacy analyses will be carried out using the Intent-to-treat Sample and Per-Protocol Sample.

7.1.1 Analysis of primary outcome variable

Efficacy analysis at the end of the study

The primary outcome measure for assessing effectiveness of ZNS (100 mg PO) post-shooting compared to the placebo group will be the proportion of officers with TTS defined as PTS positive 30 days (+/- 3 days) after shooting range exposure.

Audiogram will be performed to look for PTS. Officers for whom the difference at any frequency from 2-6 kHz in hearing thresholds (30 days (+/- 3 days) post-shooting - Baseline) is ≥ 10 dB HL will be defined as PTS positive. Primary analysis and sensitivity analyses will be carried out on the primary endpoint.

Primary analysis

Frequency and relative frequency will be used to describe the distribution of the primary outcome measure in each study group. To assess efficacy, Fisher's exact test will be used to compare the proportion of officers with PTS positive in ZNS group with the proportion of officers with PTS positive in the placebo group.

The confidence intervals will be calculated using method 10 described by Newcombe RG, 1998 and also described by Altman et al.

1. Altman, Douglas, et al., eds. Statistics with confidence: confidence intervals and statistical guidelines. <https://www.amazon.com/Statistics-Confidence-Intervals-Statistical-Guidelines/dp/0727913751>

Let n_1 be the number of participants in placebo group, and r_1 the number of participants with PTS in the placebo group. $p_1=r_1/n_1$ be the proportion of PTS in the placebo group, and q_1 the proportion of participants that do not have PTS in placebo group.

l_1 and u_1 are the lower and upper limits of the $100(1-\alpha)\%$ confidence interval for p_1

Using Wilson method we calculate:

$$A_1 = 2r_1 + z^2$$

$$B_1 = z\sqrt{z^2 + 4r_1 q_1}$$

$$C_1 = 2(n_1 + z^2)$$

$$l_1 = \frac{(A_1 - B_1)}{C_1} \quad u_1 = \frac{(A_1 + B_1)}{C_1}$$

z_α = the $100(1 - \alpha)^{th}$ percentile of the standard Normal distribution.

Let n_2 be the number of participants in ZNS group, and r_2 the number of participants with PTS in the ZNS group. $p_2 = r_2/n_2$ be the proportion of PTS in the ZNS group, and q_2 the proportion of participants that do not have PTS in ZNS group.

l_2 and u_2 are the lower and upper limits of the $100(1-\alpha)\%$ confidence interval for p_2

$$A_2 = 2r_2 + z^2$$

$$B_2 = z\sqrt{z^2 + 4r_2q_2}$$

$$C_2 = 2(n_2 + z^2)$$

$$l_2 = \frac{(A_2 - B_2)}{C_2} \quad u_2 = \frac{(A_2 + B_2)}{C_2}$$

The proportion difference between groups is: $D = p_1 - p_2$

The lower (l_D) and the upper limits (u_D) of $100(1-\alpha)\%$ confidence interval for D will be calculated as:

$$l_D = D - \sqrt{(p_1 - l_1)^2 + (u_2 - p_2)^2}$$

$$u_D = D + \sqrt{(p_2 - l_2)^2 + (u_1 - p_1)^2}$$

To provide an estimate of treatment effect a supportive logistic regression analysis will be done with covariates: age, pre-existing hearing loss dichotomized to normal to minimal hearing loss and slight to mild loss, noise exposure history dichotomized to high risk and low risk, average post-shooting.

Sensitivity analysis of the primary endpoint

The potential impact of missing primary endpoint data will be explored in sensitivity analyses using multiple imputation. Two sensitivity analyses performed:

Sensitivity 1: MI analysis under the missing not at random assumption (MNAR)

Sensitivity 2: Logistic regression tipping point analysis under the assumption of data missing at random.

Sensitivity 1.

Proc MI procedure in SAS will be used to impute missing data for study treatment groups using the distribution implied by the non-missing officer data within the placebo group. The SAS code to impute data for Sensitivity analysis 1 under the MNAR assumption will be of the form:

```
PROC MI DATA=X SEED=<value> NIMPUTE=10 OUT=MI_OUT1 NOPRINT;
CLASS GROUP;
VAR AGE PTA LSurg....;
FCS LOGISTIC(PTS);
RUN;
```

Post imputation each of the imputed 10 datasets will be analyzed using the same approach as for the primary outcome measure. The estimates of the analysis of the 10 imputed datasets will be then combined following Rubin's rules using PROC MIANALYZE procedure in SAS which will be of the form:

```
PROC MIANALYZE PARMs=GMPARMS COVB=GMCOVB PARMINFO=GMPINFO WCOV BCOV
TCOV; / *dataset "gmparms" contains the estimates and associated standard errors
for the mean parameters from each of the M=10 imputed data sets.
dataset "gmcovb" contains the asymptotic covariance matrices
dataset "gmpinfo" contains parameter info*/
MODELEFFECTS INTERCEPT AGE PTA LSurg....;
RUN;
```

Sensitivity 2.

Multiple imputation will be used to impute data in each of the study groups. A progressive penalty of $\delta_i = k_i \times \log(OR)$ will be added to imputed values in ZNS arm where (i) OR is the Odds ratio estimate for ZNS as compared to Placebo from the primary logistic regression analysis and (ii) $k_i = 1, 0.95, 0.90, \dots, 0.05, 0, 1.05, 1.10, \dots$ thus k ranges from 1 (equivalent to MI approach based on MAR) to 0 (or higher), until the conclusion of the primary analysis is overturned (i.e., $p < 0.05$ is lost at, this value of k_i being the 'tipping point'). Rubin's method will be used to combine the primary endpoint treatment effects across imputations for each value, k_i , of the penalty. Forest plots will be used to graphically display the penalty value that results in loss of statistical significance.

SAS code sample for Sensitivity analysis is provided below:

```
**Step 1: Generate 10 datasets by imputing the missing data**;

PROC MI DATA=X SEED=<value> NIMPUTE=10 OUT=MI_OUT1 NOPRINT;
CLASS GROUP;
VAR AGE PTA LSurg....;
FCS LOGISTIC(PTS);
RUN;

**Step 2: Generate 10 complete datasets from the 10 monotonized datasets in Step 1 for
missing values in the drug arm,
subtract DELTA derived above from their imputed data.**;
proc mi data=YYY NIMPUTE=1 SEED=<value> OUT=YYY_shift;
by group;
class group;
var AGE PTA LSurg....;
monotone method=logistic;
mnar adjust(PTS / shift=DELTA adjustobs=(group='1'));
run;

**Step 3: Apply the primary MMRM to the 10 complete datasets in Step 2**;
proc genmod data=YYY_shift descending;
```

```
by _imputation_;
class group;
model PTS = group AGE PTA LSurg.....;
ods output GEEModPEst=gmparms;
run;

**Step 4: Obtain the pooled inference from 10 sets of estimates from Step 3**;

PROC MIANALYze PARMS=GMPARMS COVB=GMCOVb PARMINFO=GMPINFO WCOV BCOV
TCOV;
MODELEFFECTS group;
RUN;
```

7.1.2 Analysis for secondary outcome measures.

The focus of the study is to determine efficacy of ZNS for treatment of acute hearing loss based on the testing of the hypothesis for the primary outcome. In addition, we will also conduct analysis to evaluate other important audiologic measures. The secondary outcome measures are key audiological and clinical assessments of hearing loss, and include: Audiometric TTS, DPOAEs, Ultra-high frequency audiometry, ECochG, and WIN testing 30 days (+/- 3 days) after shooting, and are measured as continuous level variables. We do not plan any adjustment of alpha error for multiple comparisons.

Analysis of variance (ANCOVA) will be used for comparison of outcome measures between each of the ZNS groups and placebo study group after controlling for baseline value, age, pre-op hearing dichotomized to: normal to minimal hearing loss and slight to mild loss, noise exposure history dichotomized to: high risk and low risk, average post-shooting TTS.

Statistical analyses will be conducted using the SAS software (SAS Institute Inc., Cary, N.C.,

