2.4 Randomisation

Eligible subjects will be randomized via an interactive randomization tool (IRT) in a balanced fashion into the 2 study groups based on the randomization list generated from the study statistician using a computer algorithm written in SAS® using randomly selected blocks of sizes 2. Within each block of 2, there will be 1 subject assigned to each study group. To balance noise-exposure history across study arms we will employ stratified randomization. The subjects will be stratified based on noise exposure survey responses as described in table below, and will then be randomized to study groups. The random assignment of subjects to the different study groups will be associated with consecutively assigned study identification numbers (Study ID) which will be unique for each study participant. The stratified randomization kit list will be provided to Advanced Rx who will package and label the drug for shipment to the pharmacist for each participant. Each bottle will be labeled with the kit number, study ID, and instructions on how to take the study medication. The bottle will not contain any information of the treatment allocation.

Name	Description
1: High Noise	Screening: LENS-Q Adapted for Police Officer – 1A Or 2A Or 3A = a.Daily, Or b.Less than daily/more than weekly, Or c.Weekly, Or d.Less than weekly/more than monthly Or e.Monthly OR 1C Or 2C Or 4C \geq 5 Years
2: Low Noise	Screening: LENS-Q Adapted for Police Officer – 1A AND 2A AND 3A = f.Less than monthly/more than yearly, g.Yearly, h.Less than yearly Or i.Never OR 1C AND 2C AND 4C $<$ 5 Years

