2.7 Sample Size Determination for The Primary Efficacy Outcome Measure

Calculation of sample size for this study is based on a balanced design and a one-sided significance level of 0.025. We estimate that among officers identified as being at high risk for permanent hearing loss due to having TTS, the proportion of PTS positive officers 30 days (+/- 3 days) after shooting will be 50%. This is the proportion of PTS positive officers we expect to observe in the placebo group. Thus, for the primary outcome, we estimated that 66 officers per group will provide us with 80.5% power to detect a 50% reduction in the proportion of PTS positive officers (from 50% to 25%) at the 1-sided alpha level of 0.025. A planned total of 132 subjects is to be enrolled and randomized.

We will make all the needed efforts to eliminate drop outs, and due to short term-follow-up of the study subjects in a period we do not expect any drop-outs or lost to follow-up.

All sample size calculations were carried out using PROC POWER procedure in SAS 9.4.

3 Study Outcomes

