3.2 Primary Efficacy Outcome

The primary efficacy outcome will be the proportion of PTS positive subjects defined as the ratio of PTS-positive subjects to total number of subjects in each study arm/group. PTS positive will be defined as all subjects who in audiogram are identified as having a permanent threshold shift (PTS) of ≥ 10 dB HL increase at any frequency from 2-6 kHz after shooting as compared to baseline audiogram. A SAS code will be written to code as PTS positive all the officers for whom the difference at any frequency from 2-6 kHz in hearing thresholds (30 days (+/- 3 days) post shooting - Baseline) will be ≥ 10 dB HL in at least one of the ears. If this difference is less than 10 dB then the officers will be coded as non-PTS positive.

To date, there are no reports of ZNS being associated with hearing damage or loss, so the hypothesis for this study will be a one-sided hypothesis.

For the primary outcome measure, the null and alternative hypotheses are provided below.

Comparison of the proportion of PTS-positive subjects between ZNS group and Placebo

$$H_0: p_{ZNS} - p_{Placebo} = 0 \quad H_A: p_{ZNS} < p_{Placebo}$$

We hypothesize that ZNS will reduce the proportion of PTS-positive officers by an absolute difference of 25% as compared to placebo. Our one-sided hypothesis is supported by animal studies, and lack of any evidence of hearing loss as a side effect of ZNS in human studies.

Hypothesis testing for the primary outcome will be performed at the one-sided alpha level of 0.025.

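### The primary Fisher's exact test is conservative and ignores the randomisation strata; a stratified CMH or Boschloo test would give about 4 to 5 points more power at the same sample size

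*SAP*

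**What the plan says.** Randomisation (SAP 2.4, Protocol 5.2) uses two strata, High Noise and Low Noise: "To balance noise-exposure history across study arms we will employ stratified randomization". Allocation is 1:1 in small blocks: "Within each block of 2, there will be 1 subject assigned to each study group".

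The primary test in SAP 7.1.1, repeated in Protocol 12.2.1, has no strata: "Fisher's exact test will be used to compare the proportion of officers with PTS positive in ZNS group" with the placebo proportion. The Newcombe interval in SAP 7.1.1 is also computed from the two pooled arms. Noise history enters only as one covariate of a secondary model: "To provide an estimate of treatment effect a supportive logistic regression analysis will be done with covariates".

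SAP 7.1.1 does not give the sidedness of the final test, but SAP 3.2 does: "Hypothesis testing for the primary outcome will be performed at the one-sided alpha level of 0.025". On size, SAP 2.7 says "we estimated that 66 officers per group will provide us with 80.5% power" for 50% against 25%, and of attrition "we do not expect any drop-outs or lost to follow-up". Neither document gives the actual size of Fisher's test, or a reason for leaving the strata out of the primary comparison.

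**The concern.** Two features of the primary test cost efficiency.

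First, Fisher's test conditions on the total number of PTS-positive officers. The attainable p-values are then coarse, and the true error rate falls well below 2.5%. The unused error rate is unused power.

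Second, the plan treats noise history as prognostic, since it stratifies on it and adjusts for it in the supportive and secondary models, yet drops it from the primary comparison. If PTS risk differs between strata, balancing on them and then ignoring them makes the test more conservative still.

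At stake are a few points of power in a 132-officer trial planned at about 80%, where accrual is expected to take four years or more.

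**Working it through.** **Inputs.** 66 per arm, PTS 50% on placebo and 25% on ZNS, no attrition (SAP 2.7); one-sided 0.025 (SAP 3.2); 1:1 within stratum (SAP 2.4). Stratum shares and PTS risk by stratum are not in the documents and are assumed below.

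**The plan's own figure.** The continuity-corrected arcsine approximation to Fisher's test gives

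d = arcsin√(0.50 − 1/132) − arcsin√(0.25 + 1/132) = 0.2455

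√132 × 0.2455 = 2.821, and Φ(2.821 − 1.960) = Φ(0.861) = 80.5%.

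This matches SAP 2.7, so N was sized for Fisher. Full binomial enumeration of Fisher's test (reject if p ≤ 0.025) gives 81.3%.

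**True size of Fisher at 66 per arm** (enumeration, same PTS rate in both arms):

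| Common PTS rate | 10% | 25% | 37.5% | 50% |
|---|---|---|---|---|
| True size | 1.20% | 1.58% | 1.72% | 1.48% |

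The maximum over all rates is 1.72%.

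**What the discreteness does.** Take 33/66 positive on placebo and 21/66 on ZNS. The pooled rate is 54/132 = 0.409, so z = (12/66) / √(0.409 × 0.591 × 2/66) = 0.1818/0.0856 = 2.12, beyond 1.96. Fisher's one-sided p, the hypergeometric probability of 21 or fewer ZNS events out of 54, is 0.0255, which just fails.

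**Unstratified alternatives** (enumeration, 50% against 25%):
- Boschloo rejects when Fisher's p is at most 0.0356, the largest cut-off that keeps the maximum size at or below 2.5%. Power is 85.0%, a gain of 85.0 − 81.3 = 3.7 points.
- Chi-square without continuity correction: power 85.6%, a gain of 4.3 points.

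**Stratified CMH** (200,000 simulated trials per row). With k officers per arm and m events in a stratum, x of them on ZNS:

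Z = Σ(m/2 − x) / √Σ[m(2k − m) / (4(2k − 1))], reject if Z ≥ 1.96.

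For Low Noise share s and placebo risk gap g, High Noise risk is 0.50 + s·g and Low Noise risk is g lower. A common odds ratio sets the overall ZNS rate to 25%. Size is taken at an overall rate of 50%.

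| s | g | Power: Fisher | Chi-square | CMH | CMH − chi-square | Size: Fisher | CMH |
|---|---|---|---|---|---|---|---|
| 35% | 0 | 81.3% | 85.6% | 85.3% | −0.4 | 1.5% | 2.3% |
| 35% | 20 pts | 81.7% | 86.0% | 86.5% | +0.5 | 1.3% | 2.4% |
| 35% | 30 pts | 82.3% | 86.5% | 87.6% | +1.2 | 1.1% | 2.5% |
| 50% | 0 | 81.3% | 85.6% | 85.3% | −0.4 | 1.5% | 2.2% |
| 50% | 20 pts | 81.8% | 86.0% | 86.7% | +0.7 | 1.3% | 2.4% |
| 50% | 30 pts | 82.2% | 86.5% | 88.0% | +1.5 | 1.2% | 2.6% |

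(Differences are taken before rounding.) CMH gains 4.0 to 4.9 points over Fisher for gaps up to 20 points, and between 5 and 6 in the two 30-point rows.

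**Which feature costs the power?** Leaving Fisher for an unstratified chi-square already recovers about 4.3 points. Stratifying while staying with an exact conditional test does not: with s = 35% its power is 81.1%, 82.9% and 83.9% at gaps of 0, 20 and 30 points.

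**Limit.** These figures are for the final analysis only. With the SAP section 9 futility rule applied to Fisher p-values at 22 per arm, simulated overall power is about 73% with Fisher at the end and about 76% with chi-square at the end, against the stated 79.4%. That gap is a separate issue, but it shows why the interim statistic must change with the final one.

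**The case against.** The case for leaving the plan alone has four parts.

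- *The trial was sized for Fisher.* This stands. Test, N and 80.5% agree. A reader might infer that the trial is underpowered or its sample size wrong; at the final analysis the documents show neither.
- *Fisher guarantees the error rate and CMH does not.* This stands against CMH, whose simulated size reaches about 2.6%. It does not favour Fisher over Boschloo, which keeps size at or below 2.5% and still gains 3.7 points.
- *Noise history is already used.* It is a covariate in the supportive logistic regression, so an adjusted effect estimate is planned. That does not alter the primary test.
- *The gain from stratifying rests on assumed inputs.* This stands. High Noise is triggered by any one of several answers, so the split may be lopsided. At 90 to 95% High Noise and a 20-point gap, CMH gives 85.5 to 85.6% and chi-square 85.5 to 85.7%: no gain.

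Two other stronger readings are tempting. One is that omitting the strata causes the 4-to-5-point loss; the comparison with chi-square rules that out. The other is that an unstratified test after stratified randomisation inflates the error rate. Here it lowers it, from 1.5% to between 1.1 and 1.2% at a 30-point gap.

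**Conclusion.** The point holds as lost efficiency in a valid test. At 66 per arm Fisher's true one-sided size is at most 1.7% against a nominal 2.5%. Its power is 81.3%, against 85.0% for Boschloo and about 85 to 87% for stratified CMH (88% with an even split and a 30-point gap). To reach 85% with Fisher would take 73 per arm: 14 more officers, or 14/34 of a year (about five months) at the planned 34 a year.

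Fisher's conservatism accounts for nearly all of this. Stratification adds from about −0.4 to about +1 point over chi-square, 1.5 at the extreme; its main merit is agreement with how officers were randomised.

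The Fisher, Boschloo and chi-square figures of 81.3%, 85.0% and 85.6% rest only on the plan's own inputs. The CMH range rests on assumed stratum shares and risk gaps of 0 to 30 points, and on a common odds ratio. This is a cheap improvement, not the repair of an error.

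**What to change.** Before unblinding:

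1. In SAP 7.1.1 and Protocol 12.2.1 together, make the primary test a one-sided CMH test at 0.025, stratified by the noise stratum recorded at randomisation, without continuity correction. Report the Mantel-Haenszel risk difference with its interval in place of the unstratified Newcombe interval. If guaranteed exact size is preferred, name Boschloo's test instead.
2. Keep Fisher's test as supportive.
3. Use the same statistic in the SAP section 9 futility rule, so that both looks rest on one test, and recompute the 79.4% overall power.
4. Restate the power in SAP 2.7 and Protocol 12.3. The latter now gives both 80.5% and 84% for identical inputs.

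A side benefit of the CMH option is that the risk difference has a standard error that Rubin's rules can pool in the imputation analyses; Fisher's p-value does not.

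The cost is a short protocol and SAP amendment, with no extra officers or data. With CMH, the exact size guarantee is also given up, with simulated size up to about 2.6%.
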